7.4.6 Summary of Visits and Procedures

Table 2 summarizes the visits and procedures for the study.

8 Adverse Event Reporting

8.1 Adverse Event Definitions

An 'adverse event' refers to any undesirable clinical occurrence in a subject, whether it is considered to be device-related or not. Adverse events (AE) may be classified as 'unanticipated adverse device effects,' 'serious adverse events,' 'significant adverse events,' or 'non-significant adverse events,' as defined below.

Classification	Definition
Serious Adverse Event	Those events that are life-threatening, or result in permanent impairment of a body function, or permanent damage to a body structure or necessitate medical (therapeutic) or surgical intervention to preclude permanent impairment of a body function or permanent damage to a body structure.
Significant Adverse Event	Those non-serious adverse events that occur with contact lens usage that are not sight-threatening but are usually symptomatic and may warrant therapeutic management and /or temporary or permanent discontinuation of contact lens wear.
Non-Significant Adverse Events	Those less severe non-serious adverse events that occur with contact lens usage that are not sight-threatening, may or may not be symptomatic and may warrant palliative management, such as ocular lubricants or temporary interruption of contact lens wear.
Unanticipated Adverse Device Effect	Adverse events in a clinical trial that were not previously identified in the protocol in terms of nature, severity, or degree of incidence. An Unanticipated Serious Adverse Device Effect is an unanticipated adverse event that is serious in nature and caused by or associated with the device and is considered reportable.

AE classification, coding (for reporting to the sponsor) and examples are provided in the following table of Contact Lens Adverse Event Classification and Reporting table:

Code	Condition	Reporting
Serious Adverse Events		
01	Presumed infectious keratitis or infectious corneal ulcer	Notify sponsor as soon as possible, within 24 hours ; IRB reporting as per requirements
02	Permanent loss of ≥ 2 lines of best spectacle corrected visual acuity (BSCVA)	
03	Corneal injury that results in permanent opacification within central cornea (6mm)	
04	Uveitis or Iritis (e.g. presence of anterior segment inflammation as described in ISO 11980, Annex B)	
05	Endophthalmitis	
06	Hyphema	
07	Hypopyon	
08	Neovascularization within the central 6mm of cornea	
00	Other serious event	
Significant Adverse Events		
11	Peripheral (outside central 6mm), non-progressive, non-infectious ulcer	Notify sponsor as soon as possible, within 5 working days ; IRB reporting as per requirements
12	Symptomatic corneal infiltrative event	
13	Superior epithelial arcuate lesions (SEALs) involving epithelial split	
14	Corneal staining \geq dense coalescent staining up to 2mm in diameter (e.g. moderate, ISO 11980 grade 3)	
15	Corneal neovascularization ≥ 1.0 mm vessel penetration (e.g. \geq ISO 111980 Grade 2), if 2 grade change from baseline	
16	Any temporary loss of ≥ 2 lines BSCVA for ≥ 2 wks	
17	Any sign and/or symptom for which subject is administered therapeutic treatment or which necessitates discontinuation of lens wear for ≥ 2 weeks	
10	Other significant event	

Non-significant Adverse Events		
21	Conjunctivitis (bacterial, viral or allergic)	Notify sponsor as soon as possible, within 5 working days ; IRB reporting as per requirements
22	Papillary conjunctivitis if \geq mild scattered papillae/follicles approximately 1mm in diameter (e.g. ISO 11890 Grade 2), if 2 grade change from baseline	
23	Asymptomatic corneal infiltrative events	
24	Any sign and/or symptom for which temporary lens discontinuation for > 1 day is recommended (if not already classified)	
20	Other sign and/or symptom warranting classification as a non-significant adverse event	

NOTE: The Clariti lens is associated with a high level of conjunctival staining (grade 3 or more). Therefore, this characteristic staining will not be classified as an adverse event in this study **unless in the investigator's opinion it is severe or is associated with other adverse ocular health changes.**

[REDACTED]

[REDACTED]

[REDACTED]

[REDACTED]

[REDACTED]

[REDACTED]

[REDACTED]

[REDACTED]

[REDACTED]

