7.1 Subjects

This study will recruit at two clinical sites, the Clinical Optics Research Lab (CORL) at Indiana University and UC Berkeley Clinical Research Center (CRC). Up to 80 subjects will be dispensed across both sites with the aim of completing 60 subjects across both sites. Each subject will be given a unique ID number. Subject ID numbers will be assigned to the subjects sequentially and in ascending order, and will not be reused in the event of screen failure, subject dropout or discontinuation from the study.

Potential subjects will be identified from the investigators' clinic and research database records and/or will be actively recruited by advertisements circulated at the investigational sites as approved by the appropriate IRB.

There are no provisions for replacing subjects during the study who are discontinued from the study.

Additionally, all subjects must meet the study inclusion and exclusion criteria listed below.

Inclusion Criteria

A person is eligible for inclusion in the study if he/she:

- Has had a self-reported oculo-visual examination in the last two years.
- Is at least 18 years of age and has full legal capacity to volunteer.
- Has read and understood the information consent letter.
- Is willing and able to follow instructions and maintain the appointment schedule.
- Is correctable to a visual acuity of 20/40 or better (in each eye) with their habitual vision correction or 20/20 best-corrected.
- Currently wears soft contact lenses.
- Requires spectacle lens powers between -0.75 to -6.50 diopters sphere (0.25D steps).
- Has no more than 0.75 diopters of refractive astigmatism.
- Has clear corneas and no active ocular disease.
- Has not worn lenses for at least 12 hours before the examination.
- Has a usable pair of spectacle lenses if required for transportation to the site for the initial visit

Exclusion Criteria

A person will be excluded from the study if he/she:

- Has never worn contact lenses before.
- Has any systemic disease affecting ocular health.
- Is using any systemic or topical medications that will affect ocular health.
- Has any ocular pathology or severe insufficiency of lacrimal secretion (moderate to severe dry eyes) that would affect the wearing of contact lenses.
- Has persistent, clinically significant corneal or conjunctival staining using sodium fluorescein dye.
- Has any clinically significant lid or conjunctival abnormalities, active neovascularization or any central corneal scars.
- Is aphakic.

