7.3.7 Masking and Control of Study Materials

The contact lenses coding will be masked to both the investigator and subject.

Under normal circumstances, the mask will not be broken until all subjects have completed the study and the database is finalized. Otherwise, the mask should be broken only if a specific emergency treatment or course of action would be dictated by knowing the treatment status of the subject. In such cases, the investigator may contact CVI in an emergency to request this information. In the event the mask is broken, the sponsor must be informed as soon as possible. The date, time, and reason for the unmasking must be documented.

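### Does the adverse event note on conjunctival staining, justified only for the control lens but applied by a masked investigator, distort the safety comparison?

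*Combined protocol and SAP*

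**What the plan says.** Section 8.1 defines an adverse event broadly, as "any undesirable clinical occurrence in a subject, whether it is considered to be device-related or not". After the table of codes, a note makes an exception. Its reason is "The Clariti lens is associated with a high level of conjunctival staining (grade 3 or more"). Its consequence is "Therefore, this characteristic staining will not be classified as an adverse event in this study". Staining stays reportable when it is in the investigator's "opinion it is severe or is associated with other adverse ocular health changes".

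Section 3 identifies clariti as the control and Invigor I as the test lens. The visible part of the note names no lens or wear period to which the exemption is confined, and it says nothing about staining with Invigor I. Redacted text follows the note.

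On masking, section 7.3.7 states "The contact lenses coding will be masked to both the investigator and subject", and that outside emergencies "the mask will not be broken until all subjects have completed the study and the database is finalized".

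Three other places bear on the point. Section 2 makes the physiological response of the anterior eye the secondary variable. Section 7.1 excludes at entry anyone who "Has persistent, clinically significant corneal or conjunctival staining using sodium fluorescein dye". Section 10.2 compares slit lamp findings between lens types by paired t test.

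**The concern.** The exemption covers the study, but its justification covers one lens. Each way of reading it seems to cause trouble.

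If it applies to all eyes, grade 3 or higher conjunctival staining on the investigational lens drops out of the adverse event count when it is neither severe nor complicated, and no reason is offered for that lens. A reader who finds no such staining in the table cannot tell whether none occurred or whether it was exempted.

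If it applies to control eyes only, a masked investigator can use it only by guessing the lens. The note also tells the investigator which lens tends to stain, so the sign being classified is itself a clue. Classification could then differ by lens for reasons unrelated to the eye.

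The plan treats this sign as relevant, both through its secondary variable and through its entry criterion. At stake would be a fair side-by-side account of safety for the investigational lens.

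**Working it through.** The plan gives no rate of grade 3 or higher conjunctival staining for either lens, so no figure of its own can be reproduced and no effect size computed. The check is a comparison of sections plus two small counts.

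**1. The two readings against masking.** Classification takes place during the study, and section 7.3.7 keeps the investigator masked until after the database is final.

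| Reading of the note | Can a masked investigator apply it? | Consequence |
|---|---|---|
| Both lenses | Yes, without knowing the lens | Same rule in both wear periods; uncomplicated, non-severe staining is left out for both |
| Control lens only | No, the lens would have to be inferred | Possible differential classification |

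The note says the exemption holds in this study and names no lens. Only the first reading fits both that wording and the masking, and it is symmetric.

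**2. How much of the adverse event table is touched.** Codes listed in section 8.1:

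- serious: 01 to 08 and 00, which is 9
- significant: 11 to 17 and 10, which is 8
- non-significant: 21 to 24 and 20, which is 5
- total: 9 + 8 + 5 = 22

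Codes naming conjunctival staining: 0 of 22 (code 14 is corneal). Such staining could enter through 4 of the 22: open codes 10 and 20, and codes 17 and 24, which depend on treatment or on stopping lens wear. Cases under 17 or 24 may well be judged severe and so stay reportable. That leaves mainly 10 and 20. Code 20 reads "Other sign and/or symptom warranting classification as a non-significant adverse event", so admission is already a matter of judgement; code 10 is open in the same way. Without the note, mild staining would still not enter automatically.

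**3. Whether the finding is lost.** The note governs classification, not examination. Slit lamp biomicroscopy on the sponsor's grading scales is specified at Visit 1 (section 7.4.1), at Visit 2, at Visit 3 (7.4.3), at Visit 4 by reference to 7.4.2, and at Visit 5 by reference to 7.4.3 and again at exit. Section 7.4 describes the screening biomicroscopy as covering corneal and conjunctival staining. Appendix 2 and the contents of Table 2 are not shown, so the follow-up items cannot be confirmed, but nothing visible suggests that they differ.

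**4. Whether the paired comparison is enough.** A mean does not fix the share of subjects at grade 3 or above. On a scale starting at 0 (an assumption):

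- all subjects at grade 1: mean 1.0, share at grade 3 or above 0%
- one third at grade 3, two thirds at grade 0: mean 3 × 1/3 + 0 × 2/3 = 1.0, share 33%

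These are illustrations, not expected rates. A count by lens would therefore say more than a mean. Section 10.2 offers the mean and standard deviation only as examples of summary statistics and leaves a detailed analysis plan to the report, so a frequency table by grade and lens is open to the analysts from grades already collected.

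**5. What a change would achieve.** Stating that the note covers whichever lens is worn would leave every classification as it is under the only reading that masking allows. Adverse event counts with and without the exempted staining would require either a form for each event and each eye (section 8.2), or counting every grade 3 or higher reading as an adverse event, which codes 10 and 20 do not do.

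**The case for a change.** The strongest case for a change has three parts.

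First, symmetry in application is not the same as justification. The visible text gives a reason for the control lens and extends the benefit to the test lens without one. This is true. A related point concerns the definition of an unanticipated adverse device effect in section 8.1, which turns on what the protocol identified beforehand. The visible text identifies this staining for clariti alone, so staining on the test lens that is screened out at the adverse event step might never be considered under that heading. This stands in part. It is limited to staining that is neither severe nor accompanied by other changes, and the redacted text after the note may deal with it.

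Second, a subject who stains heavily in one period and not in the other gives the investigator a hint about the lens, and the severity exception rests on opinion with no grade attached in the visible text. That also stands. However, the hint comes from the sign itself, and stating the note's scope would not remove it. Under a rule that is the same for both lenses, a guess can matter only through the severity judgement.

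Third, the entry criterion suggests that the plan regards conjunctival staining as important. That criterion concerns persistent, clinically significant staining at eligibility and gives no grade. It does not show that mild staining during lens wear ought to be an adverse event.

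**Conclusion.** The observation is accurate, but it does not call for a change. The note leaves its scope by lens unstated in the visible text, and masking settles that scope in practice: one rule for both lenses, with no between-lens bias shown. The remaining effect is that non-severe, uncomplicated grade 3 or higher staining on the test lens may not appear in the adverse event table. That runs mainly through 2 of 22 codes, both discretionary already. The sign remains subject to slit lamp grading and to comparison by lens, and analysts can tabulate subjects at grade 3 or above without altering the plan.

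This rests on two assumptions: that follow-up biomicroscopy includes conjunctival staining as the screening examination does, and that the redacted text after the note does not confine the exemption to one lens. No numerical effect can be given, because the documents contain no staining rate for either lens. This is a gap in detail that masking and ordinary tabulation fill, and it does not alter what the trial does or concludes.

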8.2 Procedures for Adverse Events

Treatment of an adverse event will depend on its nature and severity. Based on the clinical judgment of the investigator the subject may be referred to an ophthalmologist for treatment. The investigator will attempt to determine whether the reaction is related to the test device or a result of other factors. An Adverse Event Form will be completed for each adverse event. If both eyes are involved, a separate Adverse Event Form will be completed *for each eye*. Whenever possible, the adverse event will be photo-documented.

Expenses incurred for medical treatment as part of study participation will be paid by the sponsor (bills and prescription receipts kept). The subject must be followed until resolution and a written report completed indicating the subsequent treatment and resolution of the condition.

8.3 Reporting Adverse Events

All potential Serious and Unanticipated Adverse Device Effects that are related or possibly related to subject participation will be reported to the Principal Investigator and the sponsor within 24 hours of the investigator becoming aware of the event. The Principal Investigator will report the event to the IRB as soon as possible (by fax, mail/delivery, phone, or email). All fatal or life threatening events will be reported immediately to the IRB.

Significant and Non-Significant Adverse Events will be reported to the sponsor as soon as possible, but no later than 5 working days after the occurrence.

sponsor contact details are:

[REDACTED]

8.4 Discontinuation from the Study

A subject's study participation may be discontinued at any time if, in the opinion of the sponsor or the investigator it is in the best interest of the subject. All discontinuations will be fully documented on the appropriate study forms and the Discontinuation Form will be completed.

9 Device Malfunctions

A device malfunction means the failure of the device to meet its performance specification or otherwise perform as intended. *Any defective lens that is likely to cause or contribute to a Serious Adverse Event should be reported to the Principal Investigator and the sponsor **within 24 hours** of the investigator becoming aware of the malfunction.*

Other defective lenses should be reported to the sponsor as soon as possible.

This clinical study will also ascertain satisfaction or preference with subjective attributes such as comfort, vision, or lens handling. Responses to these subjective questionnaires will not be considered as complaints or Device Malfunctions.

10 Statistical Analysis

10.1 Sample size

Approximately 80 subjects will be enrolled with a goal that approximately 60 will be completed. Based on historical clinical data a sample size of 60 completing subjects is sufficient to detect a mean difference of 0.5 (0 – 10) in subjective ratings assuming $\alpha=0.05$ and a power of 80% (Table 3).

Table 3: Sample Size Calculations

Mean individual difference in score	Mean individual standard deviation	Sample size, Power 80% ($p = 0.05$)	Sample size, Power 85% ($p = 0.05$)
0.5	1.3	56	63

10.2 Statistical analysis

De-identified data will be provided to the sponsor by each site for the sponsor to perform the analyses. Each site will only have access to the data collected at their site.

Summary statistics will be produced (e.g. mean, standard deviation). Non-inferiority testing will be performed as appropriate. Paired t test will be used to compare slit lamp biomicroscopy, lens fit and subjective scores between study lens types. Repeated Measures Analysis of Variance (ANOVA) or paired analysis will be used to compare the variables between study visits. The critical level for statistical significance will be set at $p \leq 0.05$.

All participants who were evaluated will be used in the analysis. In the event of missing data, individual data points will be excluded in the analysis and not extrapolated from the collected data. A detailed statistical analysis plan will be outlined in the report.

11 Data Quality Assurance

[REDACTED]

[REDACTED]

[REDACTED]

[REDACTED]

- [REDACTED]
- [REDACTED]
- [REDACTED]
- [REDACTED]
- [REDACTED]
- [REDACTED]

[REDACTED]

[REDACTED]

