CooperVision is evaluating the clinical performance of an investigational silicone-hydrogel lens referred to as the Invigor I (test) compared to the clariti lens (control) when worn on a daily wear basis over one-month for each lens type in a randomized, bilateral, cross-over, dispensing study.

[REDACTED]

2 Study Objective

This is a study to evaluate the clinical performance of the Invigor I lens when worn on a daily wear modality over one-month usage.

The primary variables of interest are:

- Lens surface wettability and surface deposits
- Lens fit performance

The secondary variable of interest is:

- Anterior ocular physiological response

[REDACTED]

[REDACTED]

[REDACTED]

3 Study Design

This will be a randomized, multicenter, bilateral, one month cross-over, double-masked, dispensing study comparing the Invigor I test lens against the clariti control lens. Each subject will be randomized to wear either the test or control as a matched pair first with a study duration of approximately two months. Both test and control lenses will be used in a daily wear modality for one month. There will be no planned lens replacement during the course of the one-month study unless due to lens damage/defects. It is anticipated that this study will involve up to 5 visits: Baseline (screening and dispense the first pair visit), 2-week follow-up visit for the first pair, one-month follow-up visit for the first pair and dispense the second pair, 2-week follow-up visit for the second pair, and one-month follow-up visit for the second pair and exit visit.

4 Ethics Review / Statement of Compliance

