7.4.1 Visit 1: Screening / Baseline Visit / Dispensing Pair #1

Screening / Baseline

The following evaluations will be performed to assess eligibility according to the Inclusion and Exclusion Criteria at the Screening visit:

1. The subject is expected to attend the screening / baseline visit not wearing their habitual contact lens products for at least 12 hours prior to the study visit.
2. The subject will be required to read and sign an Informed Consent Form prior to enrolment. When the subject has signed the consent form, the subject will be considered to be enrolled on to the study.
3. Subject demographics and medical history (age, sex, race and ethnicity, medical conditions, medications, allergies) will be recorded by the investigator
4. Contact lens history (own lens information, rewetting drop use, and wear time)

5. Baseline monocular high illumination, high contrast (HIHC) entrance visual acuity with habitual spectacles or spectacle refraction
6. Auto refraction/auto keratometry: Flat and Steep K readings (D)
7. Sphero-cylindrical refraction (D), and best sphere refraction (D) & monocular & binocular distance visual acuity (HIHC) (logMAR)
8. The endpoint of this over refraction will be the best objective acuity, with (-) only being given with objective acuity, not subjective acuity improvement (not to the point that the letters start to shrink in size).

[REDACTED]

[REDACTED]

11. Slit lamp biomicroscopy will be assessed according to the guidelines set out in the CVI Grading scales (Appendix 2).
12. The investigator will confirm that the subject meets the criteria set out in the inclusion criteria, and none of the exclusion criteria and is eligible to continue in the study.
13. The subject will be assigned a randomization ID and the first pair of contact lenses (either test or control) will be selected according to the randomization table.
14. Initial contact lens power chosen based on vertexed, spherical equivalent obtained from refraction. The contact lens power will be kept the same for both test and control.
15. The contact lenses will be dispensed by a research assistant / study coordinator / technician (in a manner which does not unmask the subject and investigator).

Dispensing Pair #1

1. The lenses will be inserted by the subject from the blister pack. The use of saline for rinsing prior to insertion is permitted if necessary.

[REDACTED]

[REDACTED]

[REDACTED]

[REDACTED]

[REDACTED]

[REDACTED]

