3. The lens fit will be assessed for fit acceptance (acceptable or not acceptable) and absence of lens defects. If the fit is acceptable and there are no defects, the subject will be allowed to sit for 10 minutes to allow for the lenses to settle.

4. [REDACTED]

5 [REDACTED]

6 [REDACTED]

7. [REDACTED]

8. Monocular lens surface and fit will then be assessed and graded according to the CVI grading scales (Appendix 2):

[REDACTED]

c. Lens wettability (0-4 scale)

[REDACTED]

f. Lens deposition (0-4) and deposit type

[REDACTED]

9. Monocular lens fit will be assessed and graded according to the CVI grading scales (Appendix 2). Lens fit will be video recorded in the event of poor fit.

[REDACTED]

b. Lens centration (optimal /slightly decentered, <0.5mm /extremely decentered >0.5mm, NTSI)

[REDACTED]

[REDACTED]

[REDACTED]

4. Monocular lens surface will then be assessed and graded according to CVI grading scales (Appendix 2).

[REDACTED]

c. Lens wettability (0-4 scale)

[REDACTED]

f. Lens deposition (0-4) and deposit type

[REDACTED]

5. Monocular lens fit will then be assessed and graded according to CVI grading scales (Appendix 2).

[REDACTED]

b. Lens centration (optimal /slightly decentered, <0.5mm /extremely decentered >0.5mm, NTSI)

[REDACTED]

[REDACTED]

i. Overall lens fit acceptance (0-4 scale, and yes/no) and investigator reason, if unacceptable.

[REDACTED]

[REDACTED]

7. Slit lamp biomicroscopy will be assessed according to the guidelines set out in the CVI grading scales. The same pair of contact lenses will be re-inserted.

8. The subject will be instructed to wear the study lenses for at least 8 hours per day, maximum of 16 hours per day and at least 5 days per week.

9. The subject will be discharged and reminded to return for the one-month visit.

7.4.3 Visit 3: One Month Visit Pair #1 (Day 28 ± 4)/Dispensing pair #2

Subjects will be asked to wear lenses for at least 2 hours prior to the visit appointment.

Subjects who attend without lenses in situ for at least two hours will be rescheduled.

The following procedures will be performed (any ocular measurement procedures outlined below will be carried out on each eye):

[REDACTED]

[REDACTED]

- 1. [REDACTED]
- 2. [REDACTED]
- 3. [REDACTED]
- 4. [REDACTED]
- 5. [REDACTED]
- 6. [REDACTED]
- 7. [REDACTED]
- 8. [REDACTED]
- 9. [REDACTED]
- 10. [REDACTED]
- 11. [REDACTED]
- 12. [REDACTED]
- 13. [REDACTED]
- 14. [REDACTED]
- 15. [REDACTED]

[REDACTED]

- 1. [REDACTED]
- 2. [REDACTED]

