- 3. [REDACTED]
- 4. [REDACTED]

[REDACTED]

5. Monocular lens surface will then be assessed and graded according to CVI grading scales (Appendix 2).

- [REDACTED]
- [REDACTED]
- c. Lens wettability (0-4 scale)
- [REDACTED]
- [REDACTED]

- f. Lens deposition (0-4) and deposit type
- [REDACTED]

[REDACTED]

6. Monocular lens fit will then be assessed and graded according to CVI grading scales (Appendix 2).

[REDACTED]

b. Lens centration (optimal /slightly decentered, <0.5mm /extremely decentered >0.5mm, NTSI)

[REDACTED]

[REDACTED]

[REDACTED]

[REDACTED]

[REDACTED]

[REDACTED]

[REDACTED]

i. Overall lens fit acceptance (0-4 scale, and yes/no) and investigator reason, if unacceptable.

- [REDACTED]
- [REDACTED]
8. Slit lamp biomicroscopy will be assessed according to the guidelines set out in the CVI Grading scales.
9. There will be a 10-minute wash-out before insertion of pair 2.

Lens Dispensing Pair # 2

1. The second lens pair will be applied (according to the randomization table). The contact lenses will be provided by a study coordinator/technician to maintain masking of the investigator. The lenses will be inserted by the subject from the blister pack.
2. The use of saline for rinsing prior to insertion is permitted if necessary.
3. Lens powers of the second pair will be matched with the first pair if possible.

Procedures will be repeated as detailed in Visit 1 for pair 2 from section 7.4.1 (steps 1-13 in Dispensing pair#1 section).

7.4.4 Visit 4: Two-week follow up of pair #2 (Day 14 ± 3 of pair 2)

*Subjects will be asked to wear lenses for **at least 2 hours** prior to the visit appointment. Subjects who attend without lenses in situ for at least two hours will be rescheduled.*

Procedures will be repeated as detailed from section 7.4.2 for pair 2 (steps 1-9).

7.4.5 Visit 5: One Month Visit Pair 2/Study Exit (Day 28 ± 4 of pair 2)

Subjects will be asked to wear lenses for at least 2 hours prior to the visit appointment. Subjects who attend without lenses in situ for at least two hours will be rescheduled.

Procedures will be repeated as detailed from section 7.4.3 (steps 1-8).

[REDACTED]

[figure not shown]
- 1. [REDACTED]
- 2. [REDACTED]
- 3. [REDACTED]
- 4. [REDACTED]

[REDACTED]

3. Slit lamp biomicroscopy assessment will be conducted according to the guidelines set out in the CVI Grading scales
4. Exit visual acuity with habitual spectacles or spectacle refraction (using same method and refraction as entry).

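### Section 10.2 compares the lenses without a period term; adding one is a cheap gain in precision for this two-period cross-over

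*Combined protocol and SAP*

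**What the plan says.** Section 3 describes a bilateral cross-over with one month on each lens: "Each subject will be randomized to wear either the test or control as a matched pair first".

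For the comparison of lens types, section 10.2 states: "Paired t test will be used to compare slit lamp biomicroscopy, lens fit and subjective scores between study lens types". The next sentence concerns visits, not lenses: "Repeated Measures Analysis of Variance (ANOVA) or paired analysis will be used to compare the variables between study visits". Nothing else in the visible analysis text adds a period or sequence term. Section 10.2 leaves the detailed analysis plan to the study report.

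The two pairs of lenses start under different conditions. In section 7.4.1 subjects come to Visit 1 "not wearing their habitual contact lens products for at least 12 hours prior to the study visit". In section 7.4.3: "There will be a 10-minute wash-out before insertion of pair 2". The dispensing assessments are then repeated: "Procedures will be repeated as detailed in Visit 1 for pair 2 from section 7.4.1". The one-month visits for both pairs (sections 7.4.3 and 7.4.5) share one rule, at least two hours of lens wear before the appointment.

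The lens fit items include "Lens centration (optimal /slightly decentered, <0.5mm /extremely decentered >0.5mm, NTSI") and, at follow-up, "Overall lens fit acceptance (0-4 scale, and yes/no) and investigator reason, if unacceptable".

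**The concern.** In a two-period cross-over, scores may differ between the first and second month whichever lens is worn. A plain paired t test leaves that difference in the within-subject differences, with opposite sign in the two sequences. If the completing sequences are equal in size, the lens estimate is unaffected, but the standard error is too large and the test is conservative. If they are unequal, the estimate also moves. A period term removes both effects using the same data.

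What is at stake is precision: wider confidence intervals and lower power than 60 completers allow. Some period difference is plausible at dispensing, because the starting conditions differ. The documents give no size for it.

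**Working it through.** **Inputs.** Section 10.1 and Table 3 give a difference of 0.5 on a 0–10 rating, an SD of 1.3 (read as the SD of within-subject differences), α = 0.05, and about 80 enrolled for about 60 completing. Section 7.1 says that discontinued subjects are not replaced. The period effect P (period 2 minus period 1) and the allocation ratio are assumptions.

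**1. The plan's own figure.** A two-sided paired t test has noncentrality (0.5/1.3)√n on n − 1 df. It gives 80.7% power at n = 56 and 85.2% at n = 63, and these are the smallest n that reach 80% and 85%. Table 3 is reproduced exactly. At n = 60 power is 83.4%.

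**2. The plain test with a period effect.** The test-minus-control difference has mean d − P in the test-first sequence (n1 subjects) and d + P in the control-first sequence (n2).
- Mean of all differences: d − P(n1 − n2)/n. At P = 0.5 the shift has size 0 at 30/30, 0.5 × 6/60 = 0.05 at 33/27, and 0.5 × 12/60 = 0.10 at 36/24.
- Variance at 30/30: 1.3² + P², a factor of 1 + (P/1.3)². At P = 0.5 this is 1.148, so the SD is 1.39. The precision is that of 60/1.148 ≈ 52 completers.

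**3. The adjusted analysis.** The estimate is the average of the two sequence means, with SE = ½ × 1.3 × √(1/n1 + 1/n2) on n − 2 = 58 df. It does not depend on P.
- 30/30: SE 0.1678, power 83.39% (plain test at P = 0: 83.41%)
- 33/27: SE 0.1687, power 83.0%
- 36/24: SE 0.1713, power 81.9%

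The required n stays at 56 and 63.

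**4. Power at 30/30 if 1.3 excludes period variation** (200,000 simulated trials per setting where P > 0).

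| P | Plain | Adjusted |
|---|---|---|
| 0 | 83.4% | 83.4% |
| 0.25 | 82.5% | 83.4% |
| 0.5 | 79.5% | 83.4% |
| 0.75 | 74.6% | 83.4% |

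At P = 0.5 the type I error is 3.6% v 5.0%, and the mean 95% CI width is 0.72 v 0.67.

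**5. Power if 1.3 already includes period variation.** At P = 0.5 the SD net of period is √(1.69 − 0.25) = 1.20. Adjusted noncentrality is (0.5/1.2)√60 = 3.23 on 58 df, which gives about 89%. Table 3's formula still gives 83.4% for the plain test. With the split held at exactly 30/30 it is slightly higher: (0.5 − 2.001 × 1.3/√60)/(1.2/√60) ≈ 1.06, or about 85%.

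**6. How unequal the completers might be.** No allocation ratio is visible, so two assumptions are shown.

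| Split or worse | 40/40 randomised, 20 leave at random | Simple randomisation, 60 completers |
|---|---|---|
| 33/27 | 19.6% | 52% |
| 36/24 | 0.4% | 15.5% |

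**The case against.** The strongest reply is that the paired t test is a legitimate cross-over analysis. It is unbiased with balanced sequences and errs on the conservative side. Even at P = 0.5, as large as the whole target difference, power is 79.5% against a planned 80%; at P = 0.25 the loss is about 0.9 points. That stands, and it is why the point is graded as an improvement.

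The documented difference in starting conditions bears on dispensing assessments only. The one-month visits share the same wear rule, and no passage points to a period effect there. The historical SD may already contain period variation, in which case planned power is not reduced and adjustment only adds to it. Both points stand.

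The mixed model also needs care. Lens fit and ocular grades are taken on each eye, and a model with only a subject effect would treat the two eyes within a period as independent. The fix below deals with this.

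The deferral of the detailed plan to the report does not answer the point, because it commits to no period term before the data are seen.

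A reader might infer that the plan applies a t test to centration categories and yes/no fit acceptance. The text does not clearly say so: it speaks of lens fit and scores, and a 0–4 fit acceptance score exists.

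**Conclusion.** The point holds as a low-cost gain in precision. The plan names no period term for the lens comparison, and adding one needs no new data and leaves the required sample size unchanged. The gain at 30/30 is nil at P = 0, about 4 points of power at P = 0.5 and about 9 at P = 0.75, if 1.3 excludes period variation. If 1.3 includes it, the gain at P = 0.5 is also about 4 points (85% to 89%), from a higher base. All of this rests on an assumed P and on the 0–10 subjective score behind Table 3.

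Two stronger readings are not supported. One is that the sample size is wrong: it reproduces exactly. The other is that the planned test is invalid or inflates type I error. At a realised 36/24 split with P = 0.5 its type I error is 6.9%. Averaged over splits under 40/40 allocation with random loss, it is 4.0%, below the nominal level. How often a marked imbalance would occur cannot be settled, because the allocation method is not visible.

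**What to change.** In section 10.2, for the scores now assigned to the paired t test:

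- Use one value per subject per lens at each visit. For monocular grades take the mean of the two eyes, or fit a subject-by-period random effect so that the eyes are not treated as independent.
- Fit lens, period and sequence as fixed effects and subject as random, on subjects with both lenses. This is equivalent to averaging the two sequence means of the within-subject differences. The period term does the work; the sequence term does not change the lens contrast in complete pairs.
- Report the lens difference with a 95% CI, and keep the plain paired t test as a sensitivity analysis.
- If centration categories or yes/no fit acceptance are tested between lenses, use an ordinal or binary cross-over method with the same period adjustment (for example a cumulative logit model and the Mainland-Gart test).

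The cost is a few sentences, slightly more programming and one degree of freedom. If P = 0, the loss of power is about 0.02 points at 30/30, 0.4 at 33/27 and 1.5 at 36/24. The period term does not remove carry-over, nor bias from drop-out related to the scores.
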